4.5.9 Ordinal Scale Determination

Assessment of clinical status using a 7-category ordinal scale will be recorded *prior to dosing* at baseline on Day 1 and then again once daily every morning (ideally, between 8 a.m. and 12 p.m.) *at subsequent visits* during patient hospitalization. When possible, the patient should be assessed at approximately the same time each day. The ordinal scale categories are as follows:

1. Discharged (or “ready for discharge” as evidenced by normal body temperature and respiratory rate, and stable oxygen saturation on ambient air or ≤ 2 L supplemental oxygen)
2. Non-ICU hospital ward (or “ready for hospital ward”) not requiring supplemental oxygen
3. Non-ICU hospital ward (or “ready for hospital ward”) requiring supplemental oxygen
4. ICU or non-ICU hospital ward, requiring non-invasive ventilation or high-flow oxygen
5. ICU, requiring intubation and mechanical ventilation
6. ICU, requiring ECMO or mechanical ventilation and additional organ support (e.g., vasopressors, renal replacement therapy)
7. Death

In general, patients with oxygen saturation consistently $\leq 90\%$ should be considered for escalation to a higher clinical status category, while patients with oxygen saturation consistently $\geq 96\%$ should be considered for de-escalation to a lower category.

However, actual clinical status category should be recorded on the eCRF. Please refer to the additional guidance for investigators regarding assessment of clinical status using the 7-category ordinal scale.

Patients on supplemental oxygen should be evaluated at least daily and considered for reduction or discontinuation of oxygen support. Actual changes in level of support will be at the discretion of the clinician(s) treating the patient based on the patient's overall condition and may be dictated by other clinical and non-clinical considerations.

Normal body temperature is defined as oral, rectal, axillary, temporal, or tympanic temperature 36.1°C – 38.0°C . Normal respiratory rate is defined as 12–20 breaths per minute.

4.5.10 Optional Blood Samples for Whole Genome Sequencing (Patients at Participating Sites)

At participating sites, optional blood samples will be collected from consenting patients for DNA extraction to enable whole genome sequencing (WGS) to identify variants that are predictive of response to study drug, are associated with progression to a more severe disease state, are associated with susceptibility to developing adverse events, can lead to improved adverse event monitoring or investigation, or can increase the knowledge and understanding of disease biology and drug safety. Research will be aimed at exploring inherited characteristics. The samples may be sent to one or more laboratories for analysis.

Collection and submission of blood samples for WGS is contingent upon the review and approval of the exploratory research by each site's IRB/EC and, if applicable, an appropriate regulatory body. If a site has not been granted approval for WGS, this section of the protocol (Section 4.5.10) will not be applicable at that site.

The Informed Consent Form will contain a separate section that addresses optional blood samples for WGS. A separate, specific signature will be required to document a patient's agreement to provide optional blood samples. The investigator should document whether or not the patient has given consent to participate and (if applicable) the date(s) of consent, by completing the Optional Whole Genome Sequencing Informed Consent eCRF.

Genomics is increasingly informing researchers understanding of disease pathobiology. WGS provides a comprehensive characterization of the genome and, along with clinical data collected in this study, may increase the opportunity for developing new therapeutic approaches or new methods for monitoring efficacy and safety or predicting which patients are more likely to respond to a drug or develop adverse events. Data will be analyzed in the context of this study but will also be explored in aggregate with data from other studies. The availability of a larger dataset will assist in identification and characterization of important biomarkers and pathways to support future drug development.

For sampling procedures, storage conditions, and shipment instructions, see the laboratory manual.

Blood samples collected for WGS are to be stored until they are no longer needed or until they are exhausted. However, the storage period will be in accordance with the IRB/EC-approved Informed Consent Form and applicable laws (e.g., health authority requirements).

Refer to Section 4.5.6 for details on use of samples after patient withdrawal, confidentiality standards for data, and availability of data from biomarker analyses.

4.6 TREATMENT, PATIENT, STUDY, AND SITE DISCONTINUATION

4.6.1 Study Treatment Discontinuation

Patients must permanently discontinue study treatment if they experience any of the following:

- Any medical condition that the investigator or Sponsor determines may jeopardize the patient's safety if he or she continues to receive study treatment
- Investigator or Sponsor determination that treatment discontinuation is in the best interest of the patient
- Pregnancy
- Grade ≥ 4 dermatologic *reactions* (as described in Section 5.1.3.3)
- Major adverse cardiovascular event
- Hs-troponin I or T in the "intermediate" or "indeterminate" range or hs-troponin $>$ ULN to $< 5 \times$ ULN (and above baseline) AND either reduced ejection fraction or new hypokinesis by echocardiogram or evidence of myocarditis and/or pericarditis (as described in Section 5.1.3.3)
- Hs-troponin I or T at a level indicative of myocardial ischemia, $\geq 5 \times$ ULN, or category above "intermediate" or "indeterminate" (as described in Section 5.1.3.3)
- Conventional cardiac troponin I or T $>$ ULN, if high-sensitivity immunoassay is not available locally (as described in Section 5.1.3.3)
- QTcF prolongation or torsades des pointes as described in Section 5.1.3.4, unless there is a clear alternative cause for the changes
- Grade ≥ 3 infusion-related reaction as described in Section 5.1.3.3
- Use of prohibited therapy as described in Section 4.4.3

The primary reason for study treatment discontinuation should be documented on the appropriate eCRF. Patients who discontinue study treatment will not be replaced.

Patients will remain in study and complete all study visits and assessments (with the exception of the study drug administration).

4.6.2 Patient Discontinuation from the Study

Hospitalized patients who discontinue the study prematurely should perform a study discontinuation visit. Discharged patients who discontinue study prematurely should return to the clinic for a study discontinuation visit, if possible, or have a remote (phone or video) visit.

Patients have the right to voluntarily withdraw from the study at any time for any reason. In addition, the investigator has the right to withdraw a patient from the study at any time.

Reasons for patient discontinuation from the study may include, but are not limited to, the following:

- Patient withdrawal of consent
- Study termination or site closure
- Adverse event
- Loss to follow-up

Every effort should be made to obtain a reason for patient discontinuation from the study. The primary reason for discontinuation from the study should be documented on the appropriate eCRF. If a patient requests to be withdrawn from the study, this request must be documented in the source documents and signed by the investigator. Patients who withdraw from the study will not be replaced.

If a patient withdraws from the study, the study staff may use a public information source (e.g., county records) to obtain information about survival status.

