5.3.5.9 Deaths

All deaths that occur during the protocol-specified adverse event reporting period (see Section [5.3.1](#)), regardless of relationship to study drug, must be recorded on the Adverse Event eCRF and immediately reported to the Sponsor (see Section [5.4.2](#)). This includes death attributed to progression of COVID-19 pneumonia.

MSTT1041A/UTTR1147A—Genentech, Inc.
73/Protocol GA42469, Version 4

Death should be considered an outcome and not a distinct event. The event or condition that caused or contributed to the fatal outcome should be recorded as the single medical concept on the Adverse Event eCRF. Generally, only one such event should be reported. If the cause of death is unknown and cannot be ascertained at the time of reporting, "**unexplained death**" should be recorded on the Adverse Event eCRF. If the cause of death later becomes available (e.g., after autopsy), "unexplained death" should be replaced by the established cause of death. The term "**sudden death**" should not be used unless combined with the presumed cause of death (e.g., "sudden cardiac death").

Deaths that occur after the adverse event reporting period should be reported as described in Section 5.6.

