5.6 ADVERSE EVENTS THAT OCCUR AFTER THE ADVERSE EVENT REPORTING PERIOD

The Sponsor should be notified if the investigator becomes aware of any serious adverse event that occurs after the end of the adverse event reporting period (defined as the study completion/discontinuation visit), if the event is believed to be related to prior study drug treatment. These events should be reported through use of the Adverse Event eCRF. However, if the EDC system is not available, the investigator should report these events directly to the Sponsor or its designee, either by faxing or by scanning and emailing the paper Clinical Trial Serious Adverse Event/Adverse Event of Special Interest Reporting Form using the fax number or email address provided to investigators.

5.7 EXPEDITED REPORTING TO HEALTH AUTHORITIES, INVESTIGATORS, INSTITUTIONAL REVIEW BOARDS, AND ETHICS COMMITTEES

The Sponsor will promptly evaluate all serious adverse events and adverse events of special interest against cumulative product experience to identify and expeditiously communicate possible new safety findings to investigators, IRBs, ECs, and applicable health authorities based on applicable legislation.

To determine reporting requirements for single adverse event cases, the Sponsor will assess the expectedness of these events through use of the reference safety information in the documents listed below:

Drug	Document
MSTT1041A	RO7187807 Investigator's Brochure
UTTR1147A	RO7021610 Investigator's Brochure

The Sponsor will compare the severity of each event and the cumulative event frequency reported for the study with the severity and frequency reported in the applicable reference document.

Reporting requirements will also be based on the investigator's assessment of causality and seriousness, with allowance for upgrading by the Sponsor as needed.

A DMC will monitor the incidence of the above-listed anticipated events during the study. An aggregate report of any clinically relevant imbalances that do not favor the test product will be submitted to health authorities.

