6.4.2 Secondary Efficacy Endpoints

The secondary efficacy endpoints are as follows:

- Time to improvement of at least 2 categories relative to baseline on a 7-category ordinal scale of clinical status
- Time to hospital discharge or “ready for discharge” (as evidenced by normal body temperature and respiratory rate, and stable oxygen saturation on ambient air or ≤ 2 L supplemental oxygen)
- Duration of supplemental oxygen
- Proportion of patients alive and free of respiratory failure (requiring non-invasive ventilation, high-flow oxygen, invasive mechanical ventilation, or ECMO) at Day 28
- *Clinical status assessed using a 7-category ordinal scale at Days 14 and 28*
- Incidence of invasive mechanical ventilation *or* ECMO
- Ventilator-free days to Day 28
- Incidence of ICU stay
- Duration of ICU stay
- Time to clinical failure, defined as the time to death, invasive mechanical ventilation, ICU admission, or withdrawal of care (whichever occurs first). For patients entering the study already in ICU or on invasive mechanical ventilation, clinical failure is defined as a one category worsening on the ordinal scale, withdrawal, or death.
- Mortality rate at Days 14 and 28
- *Time to clinical improvement, defined as a NEWS2 of ≤ 2 maintained for 24 hours*

The secondary endpoints will be analyzed in the mITT population. Statistical models will be adjusted for the covariates as described in Section [6.4](#).

Full details of hypothesis testing, analysis methods, type I error control, and missing data handling will be documented in the DAP.

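### Vital status is not required for dosed patients who leave the study before Day 28, so Day 14 and Day 28 mortality and the other endpoints that count death can miss deaths

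*Protocol*

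**What the plan says.** Section 6.4.2 lists "Mortality rate at Days 14 and 28" as a secondary endpoint. Death also enters three others: ordinal status at Days 14 and 28 (category 7), alive and free of respiratory failure at Day 28, and time to clinical failure.

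The collection rules for someone who leaves early are spread over several sections:

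- Sections 5.3.1 and 5.4.2.2: adverse events and serious adverse events are reported until the completion or discontinuation visit. That is Day 60, or earlier for a patient who discontinues early.
- Section 5.3.5.9: deaths within the reporting period are reported whatever their cause. For later ones, "Deaths that occur after the adverse event reporting period should be reported as described in Section 5.6".
- Section 5.6: the sponsor is to be told of a later serious event "if the event is believed to be related to prior study drug treatment".
- Section 5.5.1: an adverse event already open is followed until it resolves or stabilises, but follow-up stops at loss to follow-up or withdrawal of consent.
- Section 4.6.2: when a patient withdraws, "the study staff may use a public information source (e.g., county records) to obtain information about survival status". The same section gives "Loss to follow-up" as its own reason for discontinuation and says that "the investigator has the right to withdraw a patient from the study at any time".

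Patients who only stop study drug stay in the study for all visits (Section 4.6.1).

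**The concern.** The endpoints have a fixed horizon of Day 14 or Day 28, but mandatory collection for an early leaver ends on the day of leaving. No section reconciles the two. Patients who leave before recovering are unlikely to be a random sample of those randomised, so an unknown vital status cannot safely be treated as uninformative. Death is the outcome least open to judgement in this trial and usually the easiest to ascertain after a patient has left. The Data Analysis Plan can state how a missing vital status is to be treated, but it cannot supply the status. The matter therefore belongs in the protocol.

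**Working it through.** **Tracing the rules.** Take an inpatient who leaves the study on Day 10 and dies of COVID-19 on Day 20.

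1. The reporting period closed at the Day 10 discontinuation visit (Sections 5.3.1, 5.4.2.2), so the all-cause rule for deaths no longer applies.
2. Section 5.3.5.9 passes the death to Section 5.6. A COVID-19 death not thought related to study drug is not notifiable there.
3. Section 5.5.1 helps only if an adverse event was open on Day 10. Expected progression of COVID-19 is not recorded as an adverse event (Section 5.3.5.11), so there may be none. If consent was withdrawn or contact lost, this follow-up has ended anyway.
4. Section 4.6.2 lets staff search public records but does not require it, and sets no date at which status is to be established.

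The death counts in all Day 28 endpoints that include death, yet a site can follow every rule and never record it.

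**Size.** The protocol has no figure to reproduce: it states no leaving rate, no planning mortality and no power for mortality. The inputs are:

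- Group size: 390 × 2/6 = 130 per active arm, and 65 + 65 = 130 in the pooled placebo (Sections 6.1, 6.4).
- Background mortality: 25% (in-hospital rate, Section 1.1) and 4.3% (hospitalised series, Section 3.3.3). Section 3.3.3 also cites 1.4% in a second pneumonia series, which would lower the bottom of the range further.
- Share leaving before Day 28 with no later status: 2–10%, an assumption.
- Mortality in leavers: equal to background, or twice background, an assumption.

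Unrecorded deaths per group = 130 × share leaving × mortality in leavers.

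| Background | Leaving | Leavers at background rate | Leavers at twice the rate |
|---|---|---|---|
| 4.3% | 2% | 130 × 0.02 × 0.043 = 0.1 | 0.2 |
| 4.3% | 10% | 130 × 0.10 × 0.043 = 0.6 | 1.1 |
| 25% | 2% | 130 × 0.02 × 0.25 = 0.65 | 1.3 |
| 25% | 10% | 130 × 0.10 × 0.25 = 3.25 | 6.5 |

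**Effect on the estimated rate.** Let m be mortality in stayers, q mortality in leavers and w the share leaving. The true rate is m(1 − w) + qw. Counting leavers as alive gives m(1 − w); excluding them gives m. With m = 25%:

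- w = 5%, q = 25%: true 25.0%; counted alive 23.75%; excluded 25.0% (no bias).
- w = 5%, q = 50%: true 23.75 + 2.5 = 26.25%; counted alive 23.75%; excluded 25.0%.
- w = 10%, q = 50%: true 22.5 + 5.0 = 27.5%; counted alive 22.5%; excluded 25.0%.

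For scale, the 95% confidence half-width for a difference between two groups of 130 at 25% mortality is 1.96 × √(2 × 0.25 × 0.75 / 130) = 10.5 points. In the worst case above, the rate within one group is out by 5.0 points (counted alive) or 2.5 points (excluded). If leaving and later mortality are alike in the two groups being compared, much of this cancels in the difference.

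**The case against.** The best defence is that Section 5.6 is a safety-notification rule and does not bar recording survival as endpoint data. Section 4.6.2 authorises a survival search with no relatedness condition. That stands: the text supports only that deaths *can* be missed, since a site may choose to search. But permission to search is not a requirement.

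Second, open adverse events are followed under Section 5.5.1, and Section 5.4 requires significant new information on serious events, including a change in outcome, within 24 hours. This stands in part, within the limits shown in step 3 of the working.

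Third, Section 4.6.2 uses the verb withdraw for the investigator's decision as well as the patient's, so the search sentence can be read to cover both. That also stands. The clear gap in scope is loss to follow-up. One may argue that without a discontinuation visit the reporting period of a lost patient never closed, but nothing then tells the site to look for the outcome.

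Fourth, the exposed group is narrow. Patients who stop drug remain in follow-up (Section 4.6.1), and discharged or transferred patients are scored on the ordinal scale to Day 60, remotely if need be (Section 3.1.1, Appendix 2). Withdrawn consent is a proper limit on any search. Both points stand and keep the expected size small.

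Three stronger readings are tempting but not supported:

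- *Loss differs by arm because UTTR1147A causes skin reactions.* Those reactions lead at most to stopping treatment (Section 4.6.1 and Table 3), and such patients stay in follow-up. No rule links them to leaving the study.
- *The primary endpoint is biased.* An unrecorded death neither adds nor removes a recovery, so time to recovery is not directly affected.
- *Listing an adverse event as a reason for leaving contradicts Section 4.6.1.* Section 4.6.2 only names possible reasons, and Section 6.5 plans a summary of adverse events leading to study discontinuation.

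**Conclusion.** The point holds as a gap in required data collection. Under the protocol as written, vital status at Days 14 and 28 need not be known for a dosed patient who leaves before then. The four secondary endpoints that count death can therefore miss deaths.

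The size cannot be fixed from the documents. On the assumptions shown it runs from 0.1 to 3.3 unrecorded deaths per 130 patients if leavers die at the background rate, and up to about 6.5 if they die at twice that rate with 10% leaving. The low end is negligible; the high end would matter for a mortality estimate. How far the estimate moves depends on whether leavers are counted as alive or excluded, which is left to the Data Analysis Plan. A reader might infer that treatment comparisons are distorted, but that would need leaving, or mortality after leaving, to differ between arms, and the documents do not establish this. The case for change rests on the low cost of closing the gap.

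**What to change.** 1. Section 4.6.2: replace *may* with *will, where local law and the patient's consent permit*. Apply the check to every reason for leaving, naming loss to follow-up, and set Day 28 and Day 60 as the dates at which vital status is established, with the date of any death recorded so that Day 14 status follows.
2. Sections 5.3.5.9 and 5.6: state that all known deaths up to Day 60 in dosed patients are recorded regardless of relatedness, including after an early discontinuation visit, within the same consent limits.
3. Discontinuation visit: offer record-only follow-up to Day 28, taking ordinal category, discharge date and vital status from the hospital chart.

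The list of reasons for study discontinuation can stay as it is.

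The cost is protocol and consent wording plus brief record checks for a few patients per arm, with no added visits, procedures or patients. Some patients will decline record follow-up and local law will limit some searches, so the gap will shrink but may not close.

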4.6.3 Study Discontinuation

The Sponsor has the right to terminate this study at any time. Reasons for terminating the study may include, but are not limited to, the following:

- The incidence or severity of adverse events in this or other studies indicates a potential health hazard to patients
- Patient enrollment is unsatisfactory

The Sponsor will notify the investigator if the Sponsor decides to discontinue the study.

4.6.4 Site Discontinuation

The Sponsor has the right to close a site at any time. Reasons for closing a site may include, but are not limited to, the following:

- Excessively slow recruitment
- Poor protocol adherence
- Inaccurate or incomplete data recording
- Non-compliance with the International Council for Harmonisation (ICH) guideline for Good Clinical Practice
- No study activity (i.e., all patients have completed the study and all obligations have been fulfilled)

5. ASSESSMENT OF SAFETY

5.1 SAFETY PLAN

MSTT1041A and UTTR1147A are not approved, and clinical development is ongoing.

The safety plan for patients in this study is based on clinical experience with MSTT1041A and UTTR1147A in completed and ongoing studies. The anticipated

MSTT1041A/UTTR1147A—Genentech, Inc.

58/Protocol GA42469, Version 4

important safety risks for MSTT1041A and UTTR1147A are outlined below. Please refer to the RO7187807 (MSTT1041A) and RO7021610 (UTTR1147A) Investigator's Brochures for a complete summary of safety information.

Several measures will be taken to ensure the safety of patients participating in this study. Eligibility criteria have been designed to exclude patients at higher risk for toxicities. Patients will undergo safety monitoring during the study, including assessment of the nature, frequency, and severity of adverse events. In addition, guidelines for managing adverse events, including criteria treatment discontinuation, are provided below.

5.1.1 Risks Associated with MSTT1041A (Anti-ST2)

5.1.1.1 Identified Risks

No risks have been identified yet for MSTT1041A.

5.1.1.2 Potential Risks

5.1.1.2.1 Adverse Effects Related to Immunogenicity

Administration of MSTT1041A, a protein therapeutic, may lead to the development of anti-MSTT1041A antibodies, which could lead to adverse events and/or decreased exposure. For details about immunogenicity rates and associated adverse events, refer to the MSTT1041A Investigator's Brochure.

